1. **Risk of Seizure:** The most significant risk of rTMS highlighted by safety studies is that of seizures. Practically all cases of seizures induced by rTMS have occurred in patients with a prior history of seizure or in which rTMS is administered at much higher frequencies (10 Hz) with stimulation trains separated by short inter-train durations (59). One seizure has been reported for a female patient on psychotropic medication while stimulated at lower frequency (3 Hz) with motor threshold of 90% (ibid). However, the rate of stimulation for this patient was three times that which we will use in our study.

Rate of stimulation appears to correlate directly with risk of seizure induction. Seizures have been intentionally induced by rTMS in patients with epilepsy although, paradoxically, seizure induction using this method has often been unsuccessful (59). Seizures have also been induced in patients with stroke and other disorders involving the central nervous system following single pulse TMS (59). These patients presumably have a lower seizure threshold.

Neurocomputational Models of Auditory Hallucinations

Of note is a report suggesting that one hertz rTMS, when administered at 110% motor threshold to motor cortex, produced spread of cortical activation -- a possible early sign of seizure risk -- when the number of pulses administered exceeds fifty (Pascual-Leone et al., 1993).

Anderson et al. (2006) examined the tolerability and safety of high doses of rTMS in sleep deprivation of young healthy males by exposing the young men to 12,960 magnetic pulses a day for up to 3 days in one week (60). Despite the intense treatment regimen, Anderson et al. failed to produce significant side effects and concluded; "doses of up to 12,960 pulses per day appear safe and tolerable in healthy young men (60).

We are proposing a single TMS administration that is 11,000 pulses less than what was used in Anderson study (60). We will remain conservative, however, regarding seizure risk. Our strategy for minimizing risk of seizure induced by rTMS is twofold:

- We will screen out all patients who have had a previous seizure.
- Motor threshold will be established at the beginning of each session and the maximum stimulation strength will be 110% of motor threshold, which remains well within published safety guidelines (59).

The risks are no higher for theta burst stimulation, please see
www.ncbi.nlm.nih.gov/pmc/articles/PMC3260517/ (37).

There have been two cases of theta-burst stimulation induced seizure when targeting the insula cortex:

<https://www.ncbi.nlm.nih.gov/pmc/articles/PMC6364800/>

We do not want to deliver a stimulation associated with seizure risk to the insula. We do want to activate the insula (as a control). The 10Hz protocol is sufficient to activate the insula, and serve as a control, and there is no evidence that it induces seizures. We propose to stimulate the insula with 10Hz rTMS which is safe and well tolerated.

We use theta burst stimulation to the cerebellum in aim 2. Theta burst stimulation has been delivered to the cerebellum without seizure side effects (and with clinical benefit to patients with Schizophrenia):

<https://www.sciencedirect.com/science/article/pii/S0987705312002675>

2. **Temporary Hearing Loss:** Hearing damage that may result from the loud sound (approximately 140 dB) produced by rTMS stimulation. To date, we have encountered no evidence of hearing impairments induced by rTMS – including patients receiving stimulation at a Wernicke's site. Pascual-Leone et al. (1993) was the only study that found temporary hearing loss in 3 of 9 patients when stimulating the motor cortical areas that resolved in two of the three patients within thirty minutes (47). The third patient had an abnormal pre-stimulation audiogram and the changes were reversed in four hours. To date, we have encountered no evidence of hearing impairments induced by rTMS – including patients with schizophrenia receiving stimulation at a Wernicke's site. Pascual-Leone et al. (1993) was the only study that found temporary hearing loss in 3 of 9 patients when stimulating the motor cortical areas that resolved in two of the three patients within thirty minutes (47). The third patient had an abnormal pre-stimulation audiogram and the changes were reversed in four hours.

We will mitigate this risk by placing earplugs in the outer ear canal and sound protection headphones over the ears themselves to avoid hearing damage that may result from the loud sound (approximately 140 dB) produced by rTMS stimulation.

Neurocomputational Models of Auditory Hallucinations

The risks are no higher for theta burst stimulation, please see
<https://www.ncbi.nlm.nih.gov/pmc/articles/PMC3260517/> (37).

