Figure 4. Symptom and cognitive effects of rTMS. 4 weeks of daily TMS significantly reduced hallucinations and symptoms more generally. Furthermore, TMS significantly improved cognition

Transcranial magnetic stimulation (TMS) is a focal, non-invasive form of brain stimulation that can depolarize or hyperpolarize superficial cortical neurons in the human brain(24). Hoffman and colleagues published the first double-blind crossover study showing that 1 Hz inhibitory stimulation of the left temporo-parietal junction (TPJ) reduced auditory verbal hallucinations (AVH, voice hearing) (25). We have delivered bilateral inhibitory 1Hz TMS over the superior temporal gyrus (960 pulses daily, 5 days a week for 4 weeks) to patients (n=15) with intractable AVH. TMS significantly improved hallucinations as well as verbal cognitive function (**Figure. 4**).

Furthermore, these improvements were associated with increases in functional connectivity between the STG and insula as well as global connectivity increases in the cerebellum. Taken together, our behavioral, imaging, computational, TMS and clinical data suggest that decreasing insula activity and increasing cerebellar activity may contribute to the therapeutic response to TMS.

We propose to test whether these neural systems implement the specific computational model-derived behaviors highlighted by our recent work. We will decrease insula activity in patients with AVH and track the effects on conditioned hallucination behavior and model parameters (Aim 1). Furthermore, we will increase cerebellar responses in another independent sample of patients with AVH and track its effects on conditioned hallucination behavior and model parameters (Aim 2). In both cases, stimulation will be compared to a sham intervention.

4. Research Plan:

Abbreviations –

Clinical Assessment Interview for Negative Symptoms (CAINS(26)); Complete blood count (CBC) Comprehensive Metabolic Panel (CMP); Electrocardiogram (EKG); Human chorionic gonadotropin (hCG) Launay–Slade Hallucination Scale (LSHS); Measurement and Treatment Research to Improve Cognition in Schizophrenia (MATRICS); Positive and Negative Syndrome Scale (PANSS); Peters Delusions Inventory (PDI); Structured Clinical Interview for DSM-5 (SCID-5); Urine Toxicology (Utox)

Measures		Pre-screen Phone Screen	Screen Visit 1	Active TMS Visit 2, 3, or 4	Sham TMS Visit 2, 3, or 4	Control TMS Visit 2, 3, or 4
Clinical Assessments	CAINS(26)					

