	PANSS					
	SCID					
Physiology Analysis	CBC					
	CMP					
	EKG					
	Hearing Assessment					
	Physical Examination					
	Utox					
	Urine HCG					
Self-report	Demographics					
	LSHS					
	Medical History					
	PDI					
	Phone Screening Questionnaire					
	TMS Safety Questionnaire					
Neuro-	MATRICS Battery					

Overall Strategy: Voice hearing patient participants with a diagnosis of schizophrenia or schizoaffective disorder (confirmed by SCID-5 interview at screening) will undergo one screening interview/assessment (1 hour) and three TMS behavioral sessions during each of which participants will perform the Conditioned Hallucinations task (40 mins). On one they will receive active TMS (of insula, n=30, or cerebellum, n=70, see power calculations below). On the other two they will receive sham stimulations prior to task performance (stimulations will be delivered in a randomized counterbalanced order). Participants will be compensated \$200 for participation (\$50 per visit). All study visits will take place at the Connecticut Mental Health Center (CMHC).

Phone Screen - telephone screen that delivers study information and assesses broad eligibility via conversation (confirms that the person hears voices, that they are between 18 and 45, that they do not have a pacemaker or suffer from seizures)

Screening (at CMHC): Yale has specialty clinics for first episode and multi-episode patients that will serve as primary recruitment sources. [name] works closely with these clinics and will facilitate recruitment.

Participants will read the consent form and provide informed consent before any screening procedures commence.

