We will recruit 30 clinical voice hearers (P+H+). They will complete two parallel forms of the conditioned hallucinations task (with different visual and auditory stimuli) on two occasions, separated by a week approximately. On one occasion, participants will receive inhibitory TMS to the insula. The other, they will receive sham. All TMS will be delivered in a randomized counterbalanced order. **Hypothesis:** *Inhibiting the insula will decrease prior over-weighting.* If this computational perturbation is responsible for conditioned hallucinations, then ameliorating it with TMS that increases insula engagement will decrease conditioned hallucination responses. Furthermore, in model-based analysis, the prior weighting parameter will be reduced following active insula TMS.

Procedure. The insula is a deep structure, compared to typical cortical targets for TMS (33). We have a double-cone coil that is optimized for targeting deeper structures (33). In prior work, inhibitory 1Hz TMS has been delivered to the insula using a double cone coil, with clinical efficacy for smoking cessation(34). We propose to use exactly this procedure; after defining RMT (see above), the coil is moved forward 6 cm anterior to the motor spot and aligned symmetrically (over the lateral prefrontal cortex) and trains of pulses will be delivered at 120% of the measured RMT. We will deliver 600 continuous pulses at 1 Hz, which is designed to induce deactivation in the target region. The sham procedure (described above) will occur on a different day (separated by at least one week) but the number of pulses will be identical.

As an added control for non-specific effects, the pattern of stimulation to be applied in Aim 2 (excitatory 10Hz repetitive) will be applied to the insula (control TMS) on a third study visit.

The order of the three study visits will be randomized and counterbalanced across participants

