Aim 2: To interrogate poor belief-updating with sham-controlled excitatory TMS to the cerebellum. We will recruit a further 70 clinical voice hearers (with a diagnosis of Schizophrenia or Schizoaffective disorder). Again, they will complete parallel forms of the conditioned hallucinations task on two occasions, separated by a week. They will receive excitatory TMS over the cerebellum (and sham on the other occasion, in a randomized counterbalanced order). **Hypotheses:** *Exciting the cerebellum will increase belief-updating.* If poor *belief-updating* contributes to conditioned hallucinations, increasing cerebellum engagement should decrease conditioned hallucinations and alter the *belief-updating* model parameter compared with sham TMS.

Neurocomputational Models of Auditory Hallucinations

As an added control for non-specific effects, the pattern of stimulation to be applied in Aim 1 (inhibitory 1Hz rTMS) will be applied to the cerebellum (control TMS) on a third study visit.

The order of the three study visits will be randomized and counterbalanced across participants.

Procedure. The cerebellum is also a deep structure, compared to typical cortical targets for TMS, however, our double cone coil is able to penetrate it (35). The cerebellar vermis [-2, -52, -16] was correlated with belief updating and as such, we will target that region. Prior work has shown theta-burst stimulation of the vermis to be well tolerated in patients with schizophrenia. We will follow that published procedure(36). Using the BrainSight neuro-navigation system (Rogue Research, Quebec, Canada), loaded with an average T1 –weighted structural image from a human adult to permit targeting of the specific vermal co-ordinates. TBS will be applied at 100% of motor threshold with the standard iTBS burst pattern (3 pulses at 50-Hz repeated at a rate of 5-Hz; 20 trains of 10 bursts given with 8-s intervals; 600 pulses). Sham stimulation will be matched for number of pulses. Cerebellar TMS is a safe and tolerable procedure (37).

Analyses. Behavioral responses for each stimulation visit (active, sham, Aim 1, Aim 2) will be used to fit HGF model parameters, per the procedure that produced the data in **Figure 2**. Those parameters will be compared with paired samples t-tests comparing sham and active TMS (separately for each aim).

Neurocomputational Models of Auditory Hallucinations

[figure not shown]

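### The control-TMS visit has no planned contrast, the active-sham test has no visit term, and one passage replaces the control visit with a second sham

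*Combined protocol and SAP*

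**What the plan says.** **Visits.** The visit table in Section I.4 has separate active, sham and control columns, the last headed "Control TMS Visit 2, 3, or 4". The Aim 1 procedure adds the third visit with the words "As an added control for non-specific effects, the pattern of stimulation to be applied in Aim 2", directed at the insula. In Aim 2 the Aim 1 pattern "will be applied to the cerebellum (control TMS) on a third study visit". Both aims randomise three visits; for Aim 1, "The order of the three study visits will be randomized and counterbalanced across participants". Section II.B (Specific Stimulation Protocols) gives control settings for both aims.

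**A different description.** The Overall Strategy paragraph gives one active session and then says "On the other two they will receive sham stimulations prior to task performance". The aims summary in Section I.1 mentions only two occasions.

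**Analysis.** The Analyses paragraph says "Behavioral responses for each stimulation visit (active, sham, Aim 1, Aim 2) will be used to fit HGF model parameters", and then "Those parameters will be compared with paired samples t-tests comparing sham and active TMS (separately for each aim"). The Power paragraph also names paired t-tests. Section I.13 names an analysis of variance of TMS against sham for each aim, without factors. MATRICS scores (Section I.4, Standard Neuropsychological Measures) and medication (Section I.4, Medication; Section I.8, exclusion vi) are promised as covariates.

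**The concern.** A control condition answers a question only if some comparison uses it. If active, sham and control is the intended design, each participant attends one stimulation session that enters no stated contrast: 100 of 3 × (30 + 70) = 300 planned task sessions. Whether the effect is specific to the active pattern then has no pre-stated test.

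If the Overall Strategy paragraph is what is meant, each person has two sham values and the paired test takes one. Nothing says whether that is the first, the second or their mean.

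The plan also randomises visit order but leaves visit out of the analysis. Any drift in task scores over visits then goes into the error term. Finally, a plain paired t-test cannot carry the promised covariates, and the analysis of variance that might carry them is not specified.

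**Working it through.** **1. Inputs.** From the Power paragraph and Section I.13: d = 0.6, n = 24 (30 budgeted) for Aim 1; d = 0.36, n = 63 (70 budgeted) for Aim 2; two-sided 0.05; 80% power. I read d as the mean active-sham difference divided by the SD of that difference.

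**2. The plan's own figures.** Paired-t power is P(|T| > t(0.975, n − 1)), where T is noncentral t with parameter d√n.
- Aim 1: 0.6 × √24 = 2.939, critical value 2.069, power 80.4%.
- Aim 2: 0.36 × √63 = 2.857, critical value 1.999, power 80.3%.

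Both reproduce. At 30 and 70 the power is 88.8% and 84.4%. These sizes cover one active-sham contrast per aim and nothing else.

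**3. Effect of omitting visit.** Let scores shift by g per visit, in SDs of the paired difference (assumed). Over the six orders, active position minus sham position is ±1, ±1 or ±2. The mean is 0, so there is no bias. The variance is 2 × (1 + 1 + 4)/6 = 2, so the SD the t-test sees is k = √(1 + 2g²): 1.010, 1.086 and 1.225 at g = 0.1, 0.3 and 0.5. Putting d/k into the formula above gives the first figure in each cell; the second is from simulation.

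| g per visit | n = 24, d = 0.6 | n = 63, d = 0.36 |
|---|---|---|
| 0 | 80.4% / 80.3% | 80.3% / 80.2% |
| 0.1 | 79.6% / 79.5% | 79.5% / 79.0% |
| 0.3 | 73.6% / 74.8% | 73.6% / 75.2% |
| 0.5 | 63.3% / 65.2% | 63.2% / 66.5% |

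The loss is about 1-2, 5-7 and 14-17 points. At n = 63 and g = 0.5 it reaches about 19 (power 61%) if the orders left over after complete sets of six fall unfavourably. At the budgeted 30 and 70, g = 0.3 leaves 83.2% and 78.1%.

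With balanced orders the estimate itself is not made noisier; only its standard error is inflated by k. The true error is therefore about 2P(T > k × critical value). At g = 0.3 and n = 63, 1.086 × 1.999 = 2.17, which gives 3.4%; at g = 0.5, 1.225 × 1.999 = 2.45, which gives 1.7%. Simulated values at 24 and 63 are 3.2-3.5% and 1.6-1.8%. The test becomes conservative.

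**4. With a visit term.** Regressing the active-minus-sham difference on visit-indicator differences removes any additive visit shift by construction. Power is then the g = 0 value with n − 3 degrees of freedom: 80.0% at 24 and 80.3% at 63.

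**5. If there are two sham visits.** Var(active − mean sham) = 1 − Var(sham − sham)/4. With equal variances (assumed) this is 0.75, so d becomes 0.6/√0.75 = 0.693 and 0.36/√0.75 = 0.416. Power is about 90% in both aims, against 80% with a single sham value.

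**6. What the control contrasts can deliver.** The expected 95% half-width is t(0.975, n − 3)/√n: 0.42 SD of that difference at 24 and 0.25 SD at 63.

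**The case against.** **Two occasions.** A reader might infer three competing designs. In Section I.4 the Aim 2 text does say "they will complete parallel forms of the conditioned hallucinations task on two occasions, separated by a week", but both aims then add the third visit, so those passages complete themselves. The real conflict is the Overall Strategy paragraph; the aims summary in Section I.1 is merely incomplete.

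**An invalid result or a wrong sample size.** Neither follows. Balanced orders give no bias, the error rate stays at or below 5%, and 24 and 63 are right for the contrast they size.

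**Balance.** A reader might infer that 63 and 70, not being multiples of six, defeat the counterbalancing. They do not: at 63 each condition can fall 21 times at each visit, and at 70 active and sham can share the same visit counts (24, 23, 23).

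**Choosing a sham value.** Picking the better of two after seeing results would give about 9% error, but nothing in the documents suggests that anyone intends this.

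**Trend size.** The assumed trends may be too large. A shift of 0.5 SD per visit is 1.0 SD over three visits, larger than either planned effect. The documents report stable scores, cite test-retest work and use new stimuli at each visit. That stands as a reason not to lean on the larger losses. It does not settle the matter: the protocol's own retest data come from one hallucinating participant and five controls, and it concedes that repeated-measures studies are few.

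**Paired t-test versus analysis of variance.** On two conditions these are the same test (F = t²), and an analysis of variance could carry covariates. It is under-specified rather than absent.

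**Conclusion.** The point holds and should be fixed before analysis. Three things are established from the text alone: no contrast uses the control visit, no analysis includes visit although order is randomised, and the Overall Strategy paragraph contradicts the visit table, the Aim 1 and Aim 2 procedures and Section II.B on what the third visit is.

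The cost of leaving out visit is conditional. It is nil without a trend and material only from about 0.3 SD per visit, and these trend sizes are assumptions. The calculation also assumes visit shifts that are additive and common to all participants, with no carryover. The 90% figure for two sham visits assumes equal variances.

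**What to change.** (a) Reconcile the Overall Strategy paragraph and the Section I.1 summary with the visit table, the Aim 1 and Aim 2 procedures and Section II.B. The sponsor decides what the third visit is.

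(b) In place of the t-test/ANOVA pair, name one primary analysis per aim. Regress each person's active-minus-sham difference on two visit-indicator differences (task visits 2 and 3: +1 if active fell there, −1 if sham did, otherwise 0). The intercept is the effect, with n − 3 degrees of freedom, two-sided 0.05, in everyone with both visits analysable. Keep it as the sole primary contrast.

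(c) If the control visit is intended, report control-sham and active-control in the same way, each with its own variance and a 95% confidence interval, as secondary contrasts outside the confirmatory family. Read active-control together with control-sham, because Section II.B (Risk of Seizure) intends the insula control to activate the target. Making active-control confirmatory would be dearer: at 0.025 each and the same d (assumed), 29 and 76 are needed, and 76 exceeds the 70 budgeted.

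(d) If two sham visits are intended, pre-specify the mean of both as the sham value. The visit indicators then take +1 for active and −1/2 for sham.

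(e) Name the MATRICS and medication scores in advance and enter them, centred, in the same difference model.

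The cost is SAP wording and modest extra analysis, with no extra participants or visits. The primary test gives up two degrees of freedom, under 0.5 point of power if there is no trend, and one more for each covariate.

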The document only addresses rTMS, not theta-burst stimulation.

Neurocomputational Models of Auditory Hallucinations

For theta-burst, I will refer to:

“Researchers who employ TBS highlight that these paradigms use less pulses and shorter duration of stimulation than typical rTMS paradigms. One implication is that TBS may be safer than other frequently used rTMS trains. However, it cannot be ignored that TBS protocols employ very high frequency stimulation. It is currently unknown whether frequency, duration, or total number of pulses is a better predictor for risk of adverse events, including the risk of seizure. Current guidelines on safety of TMS (Rossi et al., 2009) do not include recommendations for the maximum duration or intensity of stimulation when applying patterned trains of stimulation such as TBS.”

The authors thus conducted a literature review of all published studies of TBS. They state:

“Of the subjects in the 67 protocols (n=1001, 776 healthy controls), the reported adverse events were

- (1) seizure in 1 healthy control subject during continuous TBS,*
- (2) mild headache in 24 subjects (20 healthy controls, 2 patients with tinnitus, and 2 patients with Parkinson’s Disease),*
- (3) nonspecific discomfort in 5 patients with tinnitus,*
- (4) mild discomfort due to cutaneous sensation and neck muscle contraction in 5 healthy control subjects, (5) worsening tinnitus in 3 tinnitus patients,*
- (5) nausea in 1 patient with Parkinson’s Disease,*
- (6) light headedness or vagal responses in 11 healthy control subjects, and*
- (7) unilateral eye pain and lacrimation in 1 healthy control subject (which ceased upon cessation of the treatment session).*

The one incident of seizure induced by TBS was described by Oberman and Pascual-Leone (2009) and occurred in a 33-year-old healthy man with no risk factors for epilepsy. The seizure occurred following approximately 50 trains (10 seconds) of TBS to the primary motor cortex at an intensity of 100% of resting motor threshold (RMT). Given this one incident of a seizure, the resulting crude risk per subject of seizure as a result of TBS is estimated as 0.1 % while the crude risk per subject of mild adverse events (encompassing the remainder of the reported events) is 5% overall and 4.8% for healthy controls”

They conclude:

“Based on our meta-analysis of the published literature, we find that both the reported symptoms and general risk of adverse events during TBS is comparable to or less than other high frequency rTMS protocols (see Rossi et al., 2009 for a review)”

They do recommend caution in administering TBS above motor threshold. However, we are planning to deliver stimulation at motor threshold.

Neurocomputational Models of Auditory Hallucinations

We are also targeting cerebellum, not motor cortex. All seizures associated with any TMS (rTMS or TBS) have been a result of motor cortex stimulation.

Finally, we are using intermittent rather than continuous stimulation (the planned stimulation has 8 seconds between bursts) – the only seizure occurred with continuous stimulation.

This specific procedure was safe and well tolerated (with no seizures) in treatment refractory patients with schizophrenia:

There were mild adverse events (headache, discomfort), however there were also improvements in cognition.

This paper has been cited 76 times and studies adopting its stimulation parameters have been conducted in depression, obsessive-compulsive disorder, Tourette's disorder, nicotine and cocaine addiction, and pathological gambling. They were reviewed in Rachid (2018) (61) who concluded, that, in these patient studies of TBS: *"Studies have not reported major adverse effects with TBS, except for mild headaches, local painful sensations, dizziness, palpitations, and nausea."*

There is evidence for seizure (2 cases) induced by TBS to insula:

<https://www.ncbi.nlm.nih.gov/pubmed/29805097>

We are not targeting Insula with TBS in either Aim 1 or Aim 2.

3. **Source:**

- a) Identify the source of the device to be used. MAGSTIM, Ltd. (Whitland, England)
- b) Is the device provided free of charge to subjects? Yes No

4. **Investigational device accountability:** *State how the PI, or named designee, ensures that an investigational device is used only in accordance with the research protocol approved by the HIC, and maintains control of the investigational device as follows:*

- a) *Maintains appropriate records, including receipt of shipment, inventory at the site, dispensation or use by each participant, and final disposition and/or the return of the investigational device (or other disposal if applicable):*
- b) *Documents pertinent information assigned to the investigational device (e.g., date, quantity, batch or serial number, expiration date if applicable, and unique code number):*
- c) *Stores the investigational device according to the manufacturer's recommendations with respect to temperature, humidity, lighting, and other environmental considerations:*
- d) *Ensures that the device is stored in a secure area with limited access in accordance with applicable regulatory requirements:*
- e) *Distributes the investigational device to subjects enrolled in the IRB-approved protocol:*

Not applicable. Device is static and sessions are administered either at the CMHC TMS Suite.

The device was installed and is serviced by MAGSTIM accredited employees.

Neurocomputational Models of Auditory Hallucinations

Access to the device is limited to those with appropriate training and approval received. All those administering TMS treatment have attended a residential training course on how to use and maintain the device.

SECTION III: RECRUITMENT/CONSENT AND ASSENT PROCEDURES
--

1. Targeted Enrollment: Give the number of subjects:

a. Targeted for enrollment at Yale for this protocol:
30 subjects for aim 1, 70 subjects for aim 2, for a total of 100.

b. If this is a multi-site study, give the total number of subjects targeted across all sites:
No, Yale is the only site.

2. Indicate recruitment methods below. Attach copies of any recruitment materials that will be used.

 Flyers	 Internet/web postings	 Radio
 Posters	 Mass email solicitation	 Telephone
 Letter	 Departmental/Center website	 Television
 Medical record review*	 Departmental/Center research boards	 Newspaper
 Departmental/Center newsletters	 Web-based clinical trial registries	 Clinicaltrials.gov
 YCCI Recruitment database	 Social Media (Twitter/Facebook):	
 Other:		

* Requests for medical records should be made through JDAT as described at
medicine.yale.edu/ycci/oncore/availableservices/datarequests.aspx

3. Recruitment Procedures:

a. *Describe how potential subjects will be identified.*

Potential participants will be recruited from the local community via advertisement, from databases of ongoing Clinical Neuroscience Research Unit projects (only those participants who have previously consented to be re-contacted by consenting during participation in prior protocols on which there are overlapping study team members), community outpatient facility contacts and among the patients being recruited under [name] existing STEP clinic protocol, patients attending the Psychosis Clinic at the Connecticut Mental Health Center, Program for Recovery and Community Health, and the Connecticut Hearing Voices Network. We will discuss with providers whether it is appropriate for a participant to take part. We will also add a research progress note to their chart.

If they have a chart at CMHC, the research note will be added to their chart.

If they do not have a chart at CMHC, a chart will be created.

b. *Describe how potential subjects are contacted.*

Potential participants will contact us, by responding – via telephone.

c. *Who is recruiting potential subjects?*

[name], [name], and our Research Assistants will recruit potential participants.

Neurocomputational Models of Auditory Hallucinations

4. Assessment of Current Health Provider Relationship for HIPAA Consideration:

Does the Investigator or any member of the research team have a direct existing clinical relationship with any potential subject?

- Yes, all subjects
- Yes, some of the subjects
- No

If yes, describe the nature of this relationship.

5. Request for waiver of HIPAA authorization: *(When requesting a waiver of HIPAA Authorization for either the entire study, or for recruitment purposes only. Note: if you are collecting PHI as part of a phone or email screen, you must request a HIPAA waiver for recruitment purposes.)***Choose one:**

- For entire study
- For recruitment/screening purposes only
- For inclusion of non-English speaking subject if short form is being used and there is no translated HIPAA research authorization form available on the University's HIPAA website at hipaa.yale.edu.

- i. *Describe why it would be impracticable to obtain the subject's authorization for use/disclosure of this data:*
- ii. *If requesting a waiver of **signed** authorization, describe why it would be impracticable to obtain the subject's signed authorization for use/disclosure of this data:*

The investigator assures that the protected health information for which a Waiver of Authorization has been requested will not be reused or disclosed to any person or entity other than those listed in this application, except as required by law, for authorized oversight of this research study, or as specifically approved for use in another study by an IRB.

Researchers are reminded that unauthorized disclosures of PHI to individuals outside of the Yale HIPAA-Covered entity must be accounted for in the "accounting for disclosures log", by subject name, purpose, date, recipients, and a description of information provided. Logs are to be forwarded to the Deputy HIPAA Privacy Officer.

6. Process of Consent/Accent: *Describe the setting and conditions under which consent/assent will be obtained, including parental permission or surrogate permission and the steps taken to ensure subjects' independent decision-making.*

After a telephone screen to determine eligibility, potential participants will be invited in for a screening visit. First, they will read and sign a consent form, after having had the opportunity to discuss with the PI, MD and other research team members.

7. Evaluation of Subject(s) Capacity to Provide Informed Consent/Accent: *Indicate how the personnel obtaining consent will assess the potential subject's ability and capacity to consent to the research being proposed.*
Participants will be given a multiple-choice test on the contents of the consent form to ensure that they have comprehended the procedures and in particular the risks involved.

Neurocomputational Models of Auditory Hallucinations

8. **Non-English-Speaking Subjects:** *Explain provisions in place to ensure comprehension for research involving non-English speaking subjects. If enrollment of these subjects is anticipated, translated copies of all consent materials must be submitted for approval prior to use.*

Non-English-speaking participants will not be recruited to the study, given the cognitive tests involved

As a limited alternative to the above requirement, will you use the short form for consenting process if you unexpectedly encounter a non-English speaking individual interested in study participation and the translation of the long form is not possible prior to intended enrollment? YES NO*

Note* If more than 2 study participants are enrolled using a short form translated into the same language, then the full consent form should be translated into that language for use the next time a subject speaking that language is to be enrolled.

Several translated short form templates are available on the HRPP website (yale.edu/hrpp) and translated HIPAA Research Authorization Forms are available on the HIPAA website (hipaa.yale.edu). If the translation of the short form is not available on our website, then the translated short form needs to be submitted to the IRB office for approval via modification prior to enrolling the subject. *Please review the guidance and presentation on use of the short form available on the HRPP website.*

If using a short form without a translated HIPAA Research Authorization Form, please request a HIPAA waiver in the section above.

9. **Consent Waiver:** In certain circumstances, the HIC may grant a waiver of signed consent, or a full waiver of consent, depending on the study. *If you will request either a waiver of consent, or a waiver of signed consent for this study, complete the appropriate section below.*

Not Requesting any consent waivers

Requesting a waiver of signed consent:

Recruitment/Screening only *(if for recruitment, the questions in the box below will apply to recruitment activities only)*

We will present the study to potential participants by telephone, and we will assess their initial eligibility via this conversation (confirm that the person hears voices, that they are between 18 and 45, that they do not have a pacemaker or suffer from seizures). If they might qualify, we will invite them in to CMHC to consider consenting. If they consent to the study, we will proceed with the screening visit procedures.

Entire Study *(Note that an information sheet may be required.)*

For a waiver of signed consent, address the following:

- *Would the signed consent form be the only record linking the subject and the research?* **YES** **NO**
- *Does a breach of confidentiality constitute the principal risk to subjects?* **YES** **NO**

OR

- *Does the research pose greater than minimal risk?* **YES** **NO**
- *Does the research include any activities that would require signed consent in a non-research context?* **YES** **NO**

 Requesting a waiver of consent:

- Recruitment/Screening only** (if for recruitment, the questions in the box below will apply to recruitment activities only)
- Entire Study**

For a full waiver of consent, please address all of the following:

- *Does the research pose greater than minimal risk to subjects?*
 - Yes – *If you answered yes, stop. A waiver cannot be granted.*
 - No
- *Will the waiver adversely affect subjects' rights and welfare?* **YES** **NO**
- *Why would the research be impracticable to conduct without the waiver?*
- *Where appropriate, how will pertinent information be returned to, or shared with subjects at a later date?*

SECTION IV: PROTECTION OF RESEARCH SUBJECTS**Confidentiality & Security of Data:**

1. *What protected health information (medical information along with the HIPAA identifiers) about subjects will be collected and used for the research?*
Demographics and information about medications and past medical history will be collected.
2. *How will the research data be collected, recorded and stored?*
Data will consist of verbal, written, or computerized ratings of sensory stimuli, questionnaires, and computerized responses to mood, cognitive and various neuropsychological assessments. All data will be kept confidential. Participant information is maintained in computer files that are password protected, and data from individuals (computer files and hard copy versions) are identified only by code. Only the primary investigator and research staff, the Yale HIC, and the National Institute of Health, which sponsors the study, will have access to these files. The data will be archived in the same manner after the research is completed. Seven years after completion of the study the identifying data will be deleted by zeroing with software as in accordance with policies and procedures as determined by Yale University.
3. *How will the digital data be stored?*

Neurocomputational Models of Auditory Hallucinations

